### REVISION CHRONOLOGY:

Version Date	Document Type	Change(s) since last version
Enter original protocol FPA	Original	n/a
Enter protocol amendment FPA	Amendment 01	e.g. Addition of exclusion criteria

Description: *Pediatric Ease of Use Items*

Unique Identifier: *trackHO / eTrack ID*

## PROTOCOL SYNOPSIS

Unique Identifier	HO-17-18594/ 208129
Abbreviated Title	Pediatric Ease of Use Questions
GSK Product	ELLIPTA
Rationale	To develop items to assess ease of inhaler use by pediatric patients with asthma and their caregivers for implementation in clinical trials
Objectives (Primary, Secondary)	A range of devices has been developed to administer inhaled therapy for asthma, including dry powder inhaler (DPI) devices that are produced in many formats. GlaxoSmithKline (GSK) has developed and is currently marketing ELLIPTA, a DPI that is preloaded with a drug therapy to treat patients with asthma. GSK and RTI-HS have previously collaborated to develop items to assess ease of inhaler use for implementation in clinical trials of adults. In the current project, GSK would like to incorporate the previously developed questions into a clinical trial with pediatric patients (aged 5 to 11 years). A secondary objective will be to evaluate the ability of children aged 5 to 11 years to produce an audible sound using the ELLIPTA whistle.
Study Design	A cross-sectional, qualitative study including two iterative sets of cognitive interviews with 16 subjects (pediatric patients with asthma who are currently using an asthma maintenance inhaler and their caregivers).
Study Population and Sampling Methods	
Eligible subjects for the cognitive interviews must:
 
Child inclusion criteria
 
 
• Be 5 to 11 years of age
 
• Have asthma
 
• Currently use maintenance inhalers to treat their asthma
 
• Be willing and able to provide assent
 
• Be willing and able to participate in a 45-minute interview conducted in English
 
 
Caregiver inclusion criteria
 
 
• Be 18 + years of age
 
• Be a caregiver (parent or legal guardian) of a child with asthma that meets the criteria above
 
• Be willing and able to provide signed and dated informed consent and parental permission in English
 
• Be willing and able to participate in a 45-minute interview
 

Data Source	All data will be provided by the participants at the individual patient interviews and during patient recruitment.
Data Analysis Methods	
The descriptive analyses will include the computation of frequencies and percentages for categorical variables (e.g., gender, education level) and the computation of means, standard deviations, and ranges for continuous variables (e.g., current age, age at diagnosis).
 
Analysis will follow standard qualitative data-collection and analysis methods that include two main guiding principles: researcher neutrality and systematic process. Data will be systematically collected via field notes and audio recording.
 
The analysis goal of the first set of interviews is to evaluate the proposed mode of administration by age group and to identify any initial problems with item wording or response options. The analysis goal of the second set of interviews is to test the adequacy of modifications based on the first set of interviews and to inform any further revisions, inform the mode of administration by age group, and gather additional qualitative data about the final item set prior to implementation in the clinical trial. Each interview also offers an opportunity to identify any additional concepts that patients and their caregivers think should be addressed regarding ease of use (if any), contributing to the content validity of the final instrument.
 
A final report will summarize the entire questionnaire development process, including analysis methods and results.

Sample Size and Power	Target population of 16 child/caregiver dyads (32 total participants) participating in 2 sets of interviews (approximately 8 dyads per interview set). We anticipate this to be a sufficient sample size to evaluate the developed ease of use items.
Limitations	
The study design limitation rests in its qualitative nature. While data obtained from participants are considered reliable, their external validity cannot be confirmed as generalizable to the entire population of individuals with asthma who may participate in a clinical study.
 
Response bias is another potential limitation associated with the proposed design in that individuals willing to participate in a clinical trial of a new treatment may be different than those willing to participate in a qualitative study. Despite these limitations, a qualitative approach is the only study design that will meet the study objective of obtaining this data directly from individuals using inhalers to treat their asthma.

## ABBREVIATIONS

AE	adverse event
CE	concept elicitation
CFR	Code of Federal Regulations
DPI	dry powder inhaler
ePRO	electronic patient reported outcome
FDA	Food and Drug Administration
GSK	GlaxoSmithKline
ICF	informed consent form
IRA	inter-rater agreement
IRB	institutional review board
NRS	numerical rating scale
PRO	patient-reported outcome
RTI-HS	RTI Health Solutions

## **1 INTRODUCTION/BACKGROUND**

Asthma is a chronic inflammatory disorder of the airways defined by airflow obstruction. The obstruction may or may not be completely reversed with specific therapy. Airway inflammation is the result of interactions between various cells, cellular elements, and cytokines. Airway inflammation may cause recurrent or persistent bronchospasm, which causes symptoms that include wheezing, breathlessness, chest tightness, and cough, primarily at night or after exertion (Kelly et al., 2017).

Asthma affects an estimated 300 million individuals worldwide (Global Initiative for Asthma [GINA], 2017). The World Health Organization (WHO) has estimated that 13.8 million disability-adjusted life-years are lost and 346,000 asthma deaths are reported per year worldwide (GINA, 2017).

A range of devices has been developed to administer inhaled therapy for asthma, including dry powder inhaler (DPI) devices that are produced in many formats. GlaxoSmithKline (GSK) has developed and is currently marketing ELLIPTA, a DPI that is preloaded with a drug therapy to treat patients with asthma.

## **2 OBJECTIVES**

### **2.1 Primary**

The objective of the study is to revise ease of use items developed for adults (Appendix A) to be appropriate for completion by pediatric patients in future clinical trials and to evaluate the newly developed items in patients with asthma aged 5 to 11 years and their caregivers.

### **2.2 Secondary**

The secondary objective of the study is to evaluate the ability of children aged 5 to 11 years to produce an audible sound using the ELLIPTA whistle prior to use of the whistle in future clinical trials.

## **3 RESEARCH METHODOLOGY**

### **3.1 Study Design**

This cross-sectional, qualitative study will involve up to 16 child and caregiver dyads (total of 32 participants). Specifically, two iterative rounds of cognitive debriefing (targeting 8 dyads per round) will be conducted at two different qualitative research facilities that specialize in recruitment and the conduct of qualitative studies. Given the pediatric population, the proposed methods and procedures have been developed based on the recommendations provided by the International Society for Pharmacoeconomics and Outcomes Research (ISPOR) Task Force for Good Practices for the Assessment of Children and Adolescents (Matza et al., 2013). Specifically, the adult ease of use items will be modified to incorporate language appropriate for children. In addition, varying modes of administration will be assessed, including interview administration for children aged 5 to 7 years and for those who are reported by the caregiver to not be able to or to have difficulty reading. Draft pediatric and caregiver items are provided in Appendix B.

Given the age of the pediatric participants, caregivers will also be included in the interview room; however, the caregiver will be asked to sit behind the child and remain silent during the interview in order to avoid influencing the child's responses.

The interviews will be conducted by two experienced interviewers from RTI-HS. One interviewer will take primary responsibility for leading the interview while the second records detailed field notes. Field notes will incorporate both the verbal exchange between the participant and interviewer and the nonverbal cues that may influence interpretation of the data, particularly important in interviews with children. A standardized, semistructured discussion guide (Appendix C) will be used to ensure consistency of data collection across interviews. Each interview will last approximately 45 minutes. All interviews will be audio recorded and transcribed by a medical transcriptionist for use in preparing a written summary report.

Each interview will be conducted at a research facility in Raleigh, NC, or Detroit, MI; both facilities specialize in the recruitment of participants and facilitation of qualitative studies (e.g., hosting, recording).

The qualitative research facilities will identify and screen potential study subjects using a screener developed by RTI-HS in collaboration with GSK (Appendix D). Specifically, the facility staff will identify possible subjects and contact them via telephone to determine whether they are interested in participating in the study, relying on the database of individuals who expressed interest in participating in qualitative research or who have participated in prior qualitative research. If an individual is interested, he or she will be evaluated using the screener developed for this study and, if qualified, will be scheduled for an interview. Patient and caregiver demographic information (e.g., age, ethnicity) will also be collected during screening. These variables will be used to ensure a study sample that is reasonably representative of the anticipated clinical trial population. Additional variables for the purposes of stratification are not recommended given that these would limit the generalizability of the sample. Throughout the recruitment process, the qualitative research facility will provide progress updates to RTI-HS (i.e., the number and demographic characteristics of participants recruited). However, no identifying information about individual participants will be exchanged between the facility and RTI-HS.

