### **Caregiver Version**

**[The following two items are being evaluated as observer-reported outcome (ObsRO) items for children that are not able to report on ease of use or remaining doses].**

Please answer the following question based on what you observed when your child used the study inhaler (called the ELLIPTA) at home. Choose only one response for each question.

1. How easy was it for your child to use the ELLIPTA inhaler?

- Very easy
- Easy
- Difficult
- Very difficult

2. How easy was it for your child to tell how many doses were left in the ELLIPTA inhaler?

- Very easy
- Easy
- Difficult
- Very difficult

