#### **B. Explain the purpose of the interview**

*"We are doing a study to learn about what kids think of the inhalers they use for asthma. We want to figure out the best way to ask kids about using an inhaler. We will be talking to other kids like you and their parents to make questions that will be easy to answer.*

*First, I am going to ask you some questions about the inhaler that you use for your asthma and what you think about it. Then I'm going to ask you to listen to [or read for children 8-11] some questions and let me know what you think about them. There are no right or wrong answers to these questions. I just want you to tell me what you really think! When we are done, I am going to ask your [mom, dad, other caregiver] some questions about your inhaler and have them answer some questions to tell me how we can make those questions better. [Caregiver/parent will be asked to sit behind the child to avoid influencing the child's responses during the child interview portion. For the caregiver portion, there will be quiet activities such as paper and crayons available for the child while the interviewers are speaking with the caregiver].*

*Do you have any questions for me before we get started?*

*OK, let's begin..."*

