### III. Discussion with Parent

- Can you tell me about the inhaler that your child uses every day? Not the inhaler that might be called a "rescue" inhaler, but the one that is sometimes called a maintenance inhaler?
- Based on your observations, do you think that your child finds it easy or hard to use? Why?
- Do you help your child use his or her inhaler? Why or why not?
- How do you know when the inhaler is almost out of medicine? Does your child let you know? Do you check how much is left yourself? Why or why not? How often do you check?
- What else do you think is important to know about how easy or difficult it is for your child to use his or her inhaler?

Thank you for your sharing your experiences, now we would like to discuss some questions that have been developed for a research study. As part of the research study, children with asthma would be using ELLIPTA every day for a month. The children and their parents will be asked to answer questions at the end of the study about their experiences with the ELLIPTA inhaler. We would like you get your thoughts on the questions and will be asking you to read the questions out loud and tell us what you're thinking about as you answer it.

Before we begin the questions, let's start with the **instructions**.

Please answer the following question based on what you observed when your child used the study inhaler (called the ELLIPTA) at home. Choose only one response for each question.

- In your own words, what are the instructions asking you to do?
- What changes could be made to the instructions to make them clearer?

Thank you, let's go to the first question.

1. How easy was it for your child to use the ELLIPTA inhaler?

- Very easy
- Easy
- Difficult
- Very difficult

- In your own words, what is this question asking? How did you select your answer?
- Who, in your opinion, is the best person to answer this question, you or your child? Why?
- What do you think about this set of response options?
- How could this question or the response options be improved?

Let's continue to the second question.

2. How easy was it for your child to tell how many doses were left in the ELLIPTA inhaler?

- Very easy
- Easy
- Difficult
- Very difficult

- In your own words, what is this question asking? How did you select your answer?

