#### Recruitment Script

On behalf of RTI International (RTI) and a pharmaceutical company, we're recruiting children (aged 5 and 11) who use a maintenance inhaler due to their asthma. The goal of this interview study is to gain a better understanding of how children interpret and understand questions related to comparing asthma inhalers. The questions will be used in future studies evaluating inhalers.

Eligible participants and a parent/guardian will be asked to come to [FG FACILTY LOCATION], on [DATE] to participate in an interview. RTI interviewers will describe the study to both child participants as well as their parents/guardians and answer any questions. During the interview, we will ask you to remain seated behind your child (so as not to influence their responses) as the RTI interviewers speak with them. After they speak with your child, the RTI interviewers will also interview you to understand your experiences with your child's use of inhalers and ask you to review some questions developed for future studies. We will also show your child a whistle developed to teach children how to use an inhaler and ask them to try and use the whistle.

The interviews are expected to last approximately 30 minutes for each interview (up to 60 minutes total). In appreciation for your family's time, you will receive a total of \$150 (\$50 for the child participant, \$100 for the parent/guardian's time).

The interviews will be audio recorded and transcribed (without any names) to ensure the interviewers don't miss anything participants say and to help write a report summarizing the results of the interviews. The recordings will not be linked to participants' names and will be destroyed upon completion of the project. These transcripts will be given to the client, but no names or identifying information will be included.

If you still think that you and your [son/daughter] would be interested in participating in one of these interviews, I just need to ask you just a couple of questions to make sure [he or she] qualifies. Would you like to continue?

[If "Yes," please continue screening]

1 [ASK if unknown to screener] Is your child male or female?

- Male
- Female

2 What is your [your son/daughter's] current age? \_\_\_\_\_

- Aged 5 through 11 → CONTINUE
- If younger than 5 or older than 11 → STOP, does not qualify

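### Caregivers answer the two observer-reported items only after hearing the child answer on the same concepts, and nothing in the plan shows which source they used

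*Combined protocol and SAP*

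**What the plan says.** Section 3.1 states that "caregivers will also be included in the interview room" and that "the caregiver will be asked to sit behind the child and remain silent during the interview". The reason given is "in order to avoid influencing the child's responses". No reason or safeguard is given for the opposite direction, from child to caregiver.

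The order is the same wherever it is described. In Appendix C (Introduction, part B) the interviewer tells the child: "When we are done, I am going to ask your [mom, dad, other caregiver] some questions about your inhaler". The recruitment script in Appendix D tells the caregiver: "After they speak with your child, the RTI interviewers will also interview you to understand your experiences with your child's use of inhalers".

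The first two caregiver items in Appendix B ask how easy the inhaler was for the child to use, and how easy it was for the child to tell the remaining doses. They are under evaluation as observer-reported items "for children that are not able to report on ease of use or remaining doses", and their instruction asks the caregiver to answer from observation at home. In Appendix C, Section III, each is debriefed with "In your own words, what is this question asking? How did you select your answer", followed by a probe on whether the caregiver or the child is better placed to answer, and by probes on response options and improvements.

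**The concern.** An observer-reported item is useful only if the caregiver can answer it from what he or she has seen. Its stated use is for children who give no report. Here every caregiver has just listened to a child report on the same two concepts, with reasons.

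A caregiver who draws on those remarks may seem to answer the item readily, and may explain the choice with material that would not be available in the intended use. The item on remaining doses looks the more exposed. Whether a child can tell how much is left is hard to see from outside, and the child has just been asked to explain it.

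At stake is the evidence on two questions: whether caregivers can answer from observation, and who should be the reporter. Evaluation of the items in caregivers is part of the primary objective (Section 2.1) and primary endpoint (Section 3.3.1.1). The study could support an observer-reported item without having shown that caregivers can answer it unaided.

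**Working it through.** The study has no hypothesis test, and the plan states no figure to reproduce on this point. The check is to follow one dyad through the documents and count.

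1. **What the caregiver can hear.** In the Appendix C warm-up the child is asked whether the current inhaler is hard to use, and how he or she knows it is running out. The child then goes through 2 concepts × 3 formats = 6 item versions. In the four-option and yes/no formats (1a, 1b, 2a, 2b), the follow-up probes build the child's answer into the question, so it is spoken in 6 − 2 = 4 of the 6 versions. In the faces format (1c, 2c), children aged 5–7 circle the answer, and the reason is asked only if the answer changed, so it may not be spoken. Children aged 8–11 read the items aloud and are asked to say what they are thinking.

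2. **What the caregiver then answers.** Section III starts after the child's last item. It opens with general questions and then presents the two observer-reported items, on ease of use and remaining doses.

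3. **How many are exposed.** Section 3.1 gives up to 16 dyads. If the guide is followed, up to 16 of 16 caregivers are exposed and none is unexposed. Observer-reported answers given after exposure: 16 × 2 = 32 at most.

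4. **Which probes depend on the source of the answer.**
   - Affected: how the answer was selected, and who is the better person to answer.
   - Much less affected: what the question or instruction means, opinion of the response options, and suggested improvements.

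5. **Whether the plan can separate the two sources.** There is no alternate order, separate room, answer recorded before the child's interview, or probe on whether the child's remarks were used. Section 5 does not mention the point.

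**The case against.** The strongest reply is that this is cognitive debriefing. The caregiver's chosen response is not an outcome, and no child–caregiver agreement analysis is planned. Section 4 looks for problems with wording, response options, mode of administration and missing concepts, and most caregiver probes serve those aims. This stands, and it confines the point to the two probes named above.

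Second, the guide has partial safeguards. Before the items, Section III asks what the caregiver has observed about ease of use, whether the caregiver helps, and who checks the remaining medicine. The caregiver also reads the items aloud and thinks aloud. These questions do draw out an observational basis, and an answer borrowed from the child might surface. But they all come after the child's interview, and none asks directly about the source.

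Third, a reader might infer that the items are tested with exactly the information that is absent in their intended use. The documents do not support that. The child's items are reworded to the child's own maintenance inhaler, while the caregiver items keep the ELLIPTA name with no instruction to substitute. The overlap is in concept. It becomes an overlap of answer only if the caregiver is thinking of the current inhaler, which the guide does not settle.

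Fourth, nothing in the documents shows that caregivers would echo the child, and hearing the child may legitimately inform a view on who should answer. Both are fair. The difficulty is that the study could not tell.

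**Conclusion.** The concern holds as a limited design point. The sequence is fixed in the text, it applies to every dyad, and nothing in the plan distinguishes observation from recall of what the child has just said. What it weakens is the evidence on how caregivers select an answer and on who is the better reporter.

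It would be wrong to infer that the caregiver debrief as a whole is compromised, or that up to 32 outcome measurements are biased. Comprehension and response-option evidence is much less affected, and the responses themselves are not analysed as outcomes. The size of any influence cannot be estimated from the documents.

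The conclusion assumes that the guide's order is followed and that a silent caregiver in the same room can hear the child. The change is worth making before interviews begin, because it is cheap and the missing information cannot be recovered afterwards.

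**What to change.** - After consent and before the child's interview, have the caregiver mark the two observer-reported items on paper. The form should state which inhaler is being rated, and Section III should refer to the same one. It should carry the item wording in force for that interview round.
- In Section III, keep the read-aloud and think-aloud as written, then compare the answers with the marked form.
- Add one probe asking whether the answer came from the caregiver's own observation or from what the child said today. Record any change from the form and its reason.

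The cost is one form and a few extra minutes per dyad, with no extra staff. The time is an estimate, as the documents give no figure. The drawback is that the caregiver sees the item wording before the child's interview and before the Section III explanation of the planned study, so some first-reading difficulties may arise on the form. Keeping the think-aloud in Section III limits that loss. The change does not recreate the intended use, because Section 3.2.1 admits only children able to be interviewed. It does supply an answer given before the child has spoken in the interview.

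If pre-marking is not adopted, add the source probe and state the exposure as a limitation in Section 5.
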